7.2.6 FET Visit

- The time of FET visits will be determined by the status of embryo transfer and pregnancy outcomes.
- FET-1 Visit: ET(endometrial preparation, number of embryos transferred, embryo quality,etc), hCG results, clinical pregnancy results and live birth results
- FET-2 Visit: ET(endometrial preparation, number of embryos transferred, embryo quality,etc), hCG results, clinical pregnancy results and live birth results
- FET-n Visit: ET(endometrial preparation, number of embryos transferred, embryo quality,etc), hCG results, clinical pregnancy results and live birth results
- Note: The data recorded in the medical records and prescription records during subject's visit will be transcribed onto eCRF by the Investigator or suitably qualified authorized designee.
- If the procedure of FET is not conducted due to any reason, reasons should be specified and all procedures related to End of Study Visit should be performed.
- Prior to performing any trial assessments that are not part of routine medical care for the subject, the Investigator will obtain written informed consent as described in Section 9.2.

7.2.7 HCG Test

Subjects treated by ART are routinely monitored for early detection of pregnancy by measuring serum β -hCG concentration on a specific day, according to site's routine clinical practice.

After about 11 to 17 days of ET, early detection of pregnancy will be done by β -hCG blood test and the results will be recorded.

The following data will be collected:

- Date of pregnancy assessment
- Test results (positive or negative)
- Recording of AEs
- Concomitant medications prescribed and reasons.

For negative result of pregnancy and without embryos for FET, all procedures related to End of Study Visit will be performed.

For negative result of pregnancy but with embryos for FET, further FET visit will be performed.

7.2.8 Clinical pregnancy assessment

A positive test of pregnancy will be confirmed by clinical pregnancy assessment (ultrasound examination) 4 to 6 weeks after ET.

The following data will be collected:

- Date of pregnancy assessment
- Pregnancy status
- Positive pregnancy status has to be confirmed by ultrasound examination (presence or non-presence of gestational sac(s), gestational sacs with or without heartbeat, gestational stage at which ultrasound is performed is to be recorded and ectopic pregnancy).
- Gestational age
- Singleton pregnancy / multiple pregnancy
- Recording of AEs
- Concomitant medications prescribed and reasons.

If the negative of clinical pregnancy is confirmed, and without embryos for FET, all procedures related to End of Study Visit will be performed.

If the negative of clinical pregnancy is confirmed, but with embryos for FET, further FET visit will be performed.

7.2.9 Ongoing Pregnancy assessment (by telephone)

Ongoing pregnancy is defined as intrauterine pregnancy continued for 12 gestational weeks.

The following data will be collected:

- Singleton pregnancy / multiple pregnancy
- Status of ongoing pregnancy
- Early Miscarriage
- Recording of AEs
- Concomitant medications prescribed and reasons.

If the negative of ongoing pregnancy is confirmed, and without embryos for FET, all procedures related to End of Study Visit will be performed.

If the negative of ongoing pregnancy is confirmed, but with embryos for FET, further FET visit will be performed.

Once the negative of ongoing pregnancy is related to abortion, the reason of abortion should be recorded.

7.2.10 Live Birth assessment (by telephone)

The following data will be collected:

- Date of live birth
- No. of live birth(Singleton pregnancy / Multiple pregnancy)
- Type of live birth(Caesarean delivery/ Spontaneous vaginal delivery)
- Any abnormal pregnancy outcome (e.g. spontaneous abortion, congenital anomalies).
- Recording of AEs
- Concomitant medications prescribed and reasons.

If the negative of live birth is confirmed, and without embryos for FET, all procedures related to End of Study Visit will be performed.

If the negative of live birth is confirmed, but with embryos for FET, the data regarding to further FET visit should be collected.

If the negative of live birth is related to abortion, the reason of abortion should be recorded,

7.2.11 End of Study visit (by telephone)

The observation period will be completed when:

- The subject achieve a live birth in live birth visit (in either the fresh ET or the FET)
- IVF/ICSI treatment is terminated (cycle cancellation) due to:
 - Incidence of OHSS
 - Risk of OHSS
 - Lack of ovarian response to stimulation treatment
 - No oocytes retrieved
 - No fertilization
 - Other, to be specified (e.g. Investigator's or subject's decision)
- Subjects who complete 2 years follow up.
- No embryos for further FET
- Subject is lost to follow up
- AE / serious adverse event (SAE)
- There is an occurrence of an exclusion criterion
- Subject withdraws consent.

The date and reason of observation completion will be collected.

7.2.12 2 years follow up Visit (by telephone)

All subjects who don't withdraw from this study, will be followed up telephonically at the end of 2 years to check their pregnancy status and outcome.

- Date of Visit
- Fresh embryo transfer from the COS in this study(yes/no)
- FET from the COS in this study(yes/no)
- Total times of embryo transfer from the COS in this study
- Pregnancy status (yes/no), if yes
 - Gestational age
 - Singleton pregnancy / Multiple pregnancy
 - Due date
- Live birth (yes/no), if yes
 - Date of live birth
 - No. of live birth(Singleton pregnancy / Multiple pregnancy)
 - Type of live birth(Caesarean delivery/ Spontaneous vaginal delivery)
- Embryos for further FET(yes/no)

Only the Pregnancy status and live birth resulted from the COS in this study will be recorded.

7.3 Efficacy Assessments

7.3.1 Primary Endpoint

- CLBR with first live birth resulting from one initiated COS cycle

Definition of CLBR:

- Numerator is the No. of women got their first live birth; the Denominator is the No. of women who attempt the ovarian stimulation.
- There will be two ways to calculate the CLBR:
 - The conservative estimate of the cumulative live birth rate, which is based on the assumption that none of the women who do not return for a subsequent embryo transfer would have had a live birth.
 - The optimal estimate of the cumulative live birth rate, which is based on the assumption that women who do not return for a subsequent embryo transfer would have had the same live birth rates as those who do return.

7.3.2 Secondary endpoints

COS and Pregnant outcomes, including:

- Number of oocytes retrieved
- Good-quality embryo rate(The Istanbul Consensus1)
- hCG positive rate
- Implantation rate
- Clinical pregnancy rate
- Ongoing pregnancy rate
- Live birth rate
- Cumulative clinical pregnancy rate
- Miscarriage rate
- Ectopic pregnancy rate
- Cycle cancelled rate and reason
- Rate and severity of OHSS
- Time to pregnancy
- Time to live birth

7.3.3 Exploratory Endpoint

- To explore the relationship between the number of oocytes retrieved and number of embryos or times of embryo transfer or CLBR.

7.4 Assessment of Safety

Safety reporting will be conducted according to local pharmacovigilance practices.

The safety profile of the IMP will be assessed through the recording, reporting and analysis of baseline medical conditions, adverse events (AEs), physical examination findings including vital signs and laboratory tests.

Comprehensive assessment of any apparent toxicity experienced by each subject will be performed from the time of giving informed consent and throughout the trial. The investigator will report any AEs, whether observed by the Investigator or reported by the subject (see Section 7.4.1.2). The reporting period for AEs is described in Section 7.4.1.3.

7.4.1 Adverse Events

7.4.1.1 Adverse Event Definitions

Adverse Event

An AE is any untoward medical occurrence in a subject or clinical investigation subject administered a pharmaceutical product, regardless of causal relationship with this treatment. An AE can therefore be any unfavorable and unintended sign (including an abnormal laboratory finding), symptom, or disease temporally associated with the use of a medicinal product, whether or not considered related to the medicinal product.

For surgical or diagnostic procedures, the condition/illness leading to such a procedure is considered as the AE rather than the procedure itself.

The Investigator is required to grade the severity or toxicity of each AE.

Qualitative Severity (or Toxicity) Scale:

Investigators must assess the severity of AEs according to the Qualitative Toxicity Scale, as follows:

Mild: The subject is aware of the event or symptom, but the event or symptom is easily tolerated.

Moderate: The subject experiences sufficient discomfort to interfere with or reduce his or her usual level of activity.

Severe: Significant impairment of functioning: the subject is unable to carry out his or her usual activities.

Investigators must also systematically assess the causal relationship of AEs to IMP(s)/study treatment (including any other non-IMPs, radiation therapy, etc.) using the following definitions. Decisive factors for the assessment of causal relationship of an AE to the <IMP/study treatment>

include, but may not be limited to, temporal relationship between the AE and the < IMP/study treatment>, known side effects of <IMP/study treatment>, medical history, concomitant medication, course of the underlying disease, trial procedures.

Unrelated: Not reasonably related to the IMP/study treatment. AE could not medically (pharmacologically/clinically) be attributed to the IMP/study treatment under study in this clinical trial protocol. A reasonable alternative explanation must be available.

Related: Reasonably related to the IMP/study treatment. AE could medically (pharmacologically/clinically) be attributed to the IMP/study treatment under study in this clinical trial protocol.

Abnormal Laboratory Findings and Other Abnormal Investigational Findings

Abnormal laboratory findings and other abnormal investigational findings (for example, on an ECG trace) should not be reported as AEs unless they are associated with clinical signs and symptoms, lead to treatment discontinuation or are considered otherwise medically important by the Investigator. If a laboratory abnormality fulfills these criteria, the identified medical condition (for example, anemia, increased ALT) must be reported as the AE rather than the abnormal value itself.

Serious Adverse Events

An SAE is any untoward medical occurrence that at any dose:

- Results in death.
- Is life-threatening. (Note: The term “life-threatening” refers to an event in which the subject is at risk of death at the time of the event, not an event that hypothetically might have caused death if it was more severe.)
- Requires inpatient hospitalization or prolongs an existing hospitalization.
- Results in persistent or significant disability or incapacity.
- Is a congenital anomaly or birth defect.
- Is otherwise considered to be medically important. (Note: Important medical events that may not result in death, be life-threatening, or require hospitalization may be considered as SAEs when, based upon appropriate medical judgment, they may jeopardize the subject or may require medical or surgical intervention to prevent one of the outcomes listed above. Examples of such events include allergic bronchospasm requiring intensive treatment in an emergency room or at home, blood dyscrasia or convulsions that do not result in inpatient hospitalization, or the development of drug dependency or drug abuse.)

For the purposes of reporting, any suspected transmission of an infectious agent via an IMP is also considered an SAE, as described in Section 7.4.1.4

Events that Do Not Meet the Definition of an SAE

Elective hospitalizations to administer, or to simplify trial treatment or trial procedures are not considered SAEs. However, all events leading to unplanned hospitalizations or unplanned prolongation of an elective hospitalization (for example, undesirable effects of any administered treatment) must be documented and reported as SAEs.

Events Not to Be Considered as AEs/SAEs

Medical conditions present at the initial trial visit that do not worsen in severity or frequency during the trial are defined as Baseline Medical Conditions, and are not to be considered AEs.

7.4.1.2 Methods of Recording and Assessing Adverse Events

At each trial visit, the subject will be queried on changes in her condition. During the reporting period, any unfavorable changes in the subject's condition will be recorded as AEs, whether reported by the subject or observed by the investigator.

Complete, accurate and consistent data on all AEs experienced for the duration of the reporting period (defined below) will be reported on an ongoing basis in the appropriate section of the eCRF. All SAEs must be additionally documented and reported using the appropriate Report Form as described in Section 7.4.1.4.

Specific guidance can be found in the eCRF Completion and Monitoring Conventions provided by the Sponsor.

7.4.1.3 Definition of the Adverse Event Reporting Period

The AE reporting period for safety surveillance begins when the subject is initially included in the trial (date of first signature of informed consent/date of first signature of first informed consent) and continues until the end of trial visit.

Any SAE assessed as related to IMP must be reported whenever it occurs, irrespective of the time elapsed since the last administration of IMP

7.4.1.4 Procedure for Reporting Serious Adverse Events, Adverse Events of Special Interest and Dose Limiting Toxicities

Serious Adverse Events

In the event of any new SAE occurring during the reporting period, the Investigator must immediately (within a maximum of 24 HOURS after becoming aware of the event) inform the Sponsor or its designee in writing. All written reports should be transmitted using the SAE Report Form, which must be completed by the Investigator following specific completion instructions.

In exceptional circumstances, an SAE (or follow-up information) may be reported by telephone; in these cases, a written report must be sent immediately thereafter by fax or e-mail. Names,

addresses, and telephone and fax numbers for SAE reporting will be included in the trial-specific SAE Report Form.

Relevant pages from the eCRF may be provided in parallel (for example, medical history, concomitant drugs). Additional documents may be provided by the Investigator, if available (for example, laboratory results, hospital report, and autopsy report). In all cases, the information provided on the SAE Report Form must be consistent with the data about the event recorded in the eCRF.

The Investigator must respond to any request for follow-up information (for example, additional information, outcome, final evaluation, other records where needed) or to any question the Sponsor/designee may have on the AE within the same timelines as those noted above for initial reports. This is necessary to ensure prompt assessment of the event by the Sponsor or designee and (as applicable) to allow the Sponsor to meet strict regulatory timelines associated with expedited safety reporting obligations.

7.4.1.5 Safety Reporting to Health Authorities, Independent Ethics Committees/ Institutional Review Boards and Investigators

The Sponsor will send appropriate safety notifications to Health Authorities in accordance with applicable laws and regulations.

The Investigator must comply with any applicable site-specific requirements related to the reporting of SAEs (particularly deaths) involving trial subjects to the IEC/IRB that approved the trial.

In accordance with ICH GCP and local GCP, the Sponsor/designee will inform the Investigator of “findings that could adversely affect the safety of subjects, impact the conduct of the trial or alter the IEC’s/IRB’s approval/favorable opinion to continue the trial.” In particular and in line with respective regulations, the Sponsor/designee will inform the Investigator of AEs that are both serious and unexpected and are considered to be related to the administered product (“suspected unexpected serious adverse reactions” or SUSARs). The Investigator should place copies of Safety Reports in the Investigator Site File. National regulations with regard to Safety Report notifications to Investigators will be taken into account.

When specifically required by regulations and guidelines, the Sponsor/designee will provide appropriate Safety Reports directly to the concerned lead IEC and will maintain records of these notifications. When direct reporting is not clearly defined by national or site-specific regulations, the Investigator will be responsible for promptly notifying the concerned IEC of any Safety Reports provided by the Sponsor/designee and of filing copies of all related correspondence in the Investigator Site File.

The Sponsor’s responsibilities regarding the reporting of SAEs/SUSARs/Safety Issues will be carried out in accordance with that Directive and with the related Detailed Guidance documents.

7.4.1.6 Monitoring of Subjects with Adverse Events

AEs are recorded and assessed continuously throughout the trial (see Section 7.4.1.3) and are assessed for final outcome at the end of trial visit must be monitored and followed up by the Investigator until stabilization or until the outcome is known, unless the subject is documented as “lost to follow-up”. Reasonable attempts to obtain this information must be made and documented. It is also the responsibility of the Investigator to ensure that any necessary additional therapeutic measures and follow-up procedures are performed.

7.4.2 Pregnancy and In Utero Drug Exposure

Not applicable

7.4.3 Clinical Laboratory Assessments

Anti-Mullerian hormone (AMH) analysis will be performed in central lab.

Other lab data such as hematology, biochemistry and urinalysis laboratory in each site will be used and normal ranges of laboratory examinations will be provided by each site.

7.4.4 Vital Signs, Physical Examinations, and Other safety Assessments

Routine clinical examination will be performed.

7.5 Pharmacokinetics

Not applicable

7.6 Biomarkers

Anti-Mullerian hormone (AMH)

The result of AMH test will be used in final statistical analysis.

7.7 Other Assessments

Not applicable

8 Statistics

8.1 Sample Size

For this non-inferiority trial, a sufficient number of subjects will be enrolled to have at least 80% power to demonstrate the non-inferiority of GnRH antagonist protocol vs GnRH agonist protocol regarding the CLBR using a two-sided 95% confidence interval. The CLBR is expected to be 60% in both groups, and the non-inferiority margin is -10% (absolute). Based on these assumptions, a

sample size of 377 evaluable subjects per arm would provide 80% power to demonstrate the non-inferiority of GnRH antagonist protocol vs GnRH agonist protocol regarding the CLBR. As a result, totally about 888 subjects will be randomized, that is 444 for each treatment group after considering 15% dropout rate.

8.2 Randomization

Subjects will be randomized at a 1:1 ratio to GnRH-a group and GnRH-ant group.

The trial is designed as a multicenter trial, and randomization will be conducted by using the IWRS.

Randomization numbers will be computer generated by a statistician at FMD. Sites will log into EDC system to have randomization numbers assigned according to the sequence of screening. A unique randomization number will be allocated to the subject together with the assignment of the group.

8.3 Endpoints

8.3.1 Primary Endpoints

- CLBR with first live birth resulting from one initiated COS cycle

8.3.2 Secondary Endpoints

COS and pregnant outcomes, including:

- Number of oocytes retrieved
- Good-quality embryo rate(The Istanbul Consensus1)
- hCG positive rate (in fresh cycle)
- Implantation rate (in fresh cycle)
- Clinical pregnancy rate (in fresh cycle)
- Ongoing pregnancy rate(in fresh cycle)
- Live birth rate(in fresh cycle)
- Cumulative clinical pregnancy rate
- Miscarriage rate(in fresh cycle)
- Ectopic pregnancy rate(in fresh cycle)
- Cycle cancelled rate and reason(in fresh cycle)
- Rate and severity of OHSS(in fresh cycle)
- Time to pregnancy
- Time to live birth

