Both GnRH agonist and GnRH antagonist protocols are widely used in controlled ovarian stimulation (COS); however, there is a persistent debate concerning the reproductive outcomes when comparing the two analogue treatments (Toftager M, 2016). In the most recent Cochrane review, the GnRH antagonist protocol was associated with comparable live birth rate (LBR) and a substantial reduction in the incidence of OHSS when compared to GnRH agonist long protocol in women undergoing ART in none selected population (Hesham G AI,2016).

Comparing with GnRH agonist protocol, the GnRH antagonist protocol is associated with fewer oocytes retrieved, lower OHSS incidence whereas the ongoing pregnancy rate and LBR were similar in supposed normal responders in the recent systematic review and meta-analysis (JS Xiao, 2014). However, the data published in the same year found that among good-prognosis patients, agonist protocol decreased cancellation risk and increased odds of implantation and live birth compared with antagonist protocol using the national surveillance data (D. Grow, 2014).

Overall, there is an ongoing debate regarding the superiority of these two COS protocols in supposed normal responders.

In the other aspect, IVF success has generally been calculated and reported on the basis of LBRs per treatment attempt involving either an intended fresh or frozen-thawed embryo transfer (FET). The continued improvement in reproductive technology has seen an increase in the number of FETs and their associated pregnancy rates. This, combined with an emphasis on reducing multiple pregnancies and increasing single embryo transfers (SETs), means that outcomes per fresh embryo transfer are no longer meaningful to patients and clinicians who want to know their chance of live birth over an entire IVF program. The most appropriate way of reporting this is to estimate the

cumulative chances of success per woman after a number of complete cycles—defined as all fresh and FET attempts resulting from one episode of ovarian stimulation. CLBRs are increasingly proving to be the currency of IVF (DJ. McL 2016).

From fertility counselling perspective, patients undergoing IVF treatments should be informed not only the opportunity of success rate in fresh cycle transfer but also the probability to achieve a live birth after utilization of all cryopreserved embryos.

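### OHSS rate and severity is a fresh-cycle endpoint, but the schedule assesses OHSS only on triggering day and at oocyte pick-up, and no OHSS definition or grading scale is given

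*Combined protocol and SAP*

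**What the plan says.** - **Endpoint.** Sections 8.3.2 and 8.5.3 include "Rate and severity of OHSS(in fresh cycle" among the secondary endpoints. Section 7.3.2 lists "Rate and severity of OHSS" without the fresh-cycle restriction.
- **Schedule (Table X).** The OHSS row is ticked at triggering day and oocyte pick-up only. The AE row runs on through fresh embryo transfer, hCG test, clinical pregnancy, ongoing pregnancy and live birth; it is blank at frozen embryo transfer (FET).
- **Eliciting AEs.** Section 7.4.1.2: "At each trial visit, the subject will be queried on changes in her condition". Section 8.5.4 also provides for questioning. The reporting period starts at consent and "continues until the end of trial visit" (Section 7.4.1.3).
- **Grading.** Section 7.4.1.1: "Investigators must assess the severity of AEs according to the Qualitative Toxicity Scale". That scale is mild, moderate or severe, judged by tolerability and effect on usual activity. The endpoint definitions in Section 8.5.3 do not cover OHSS.
- **Other routes.** An event that "Requires inpatient hospitalization or prolongs an existing hospitalization" is an SAE. Section 7.2.11 includes "Incidence of OHSS" among the reasons for terminating treatment.
- **Blinding.** The trial is open-label (Section 5.4), and Section 6.10 marks blinding as not applicable.

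**The concern.** The endpoint covers the fresh cycle, which the plan itself follows through transfer, hCG test and pregnancy assessment. The OHSS assessment stops much earlier: one tick falls on the day of the trigger and the other comes before transfer. For the rest of the fresh cycle nobody is asked about OHSS by name, and a case that is mentioned gets a general AE severity, which is not an OHSS grade.

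What is at stake is the OHSS comparison. Sections 3 and 5.2 cite a review that found "a substantial reduction in the incidence of OHSS when compared to GnRH agonist long protocol", and safety is part of the secondary objective, so readers will look at this result. If mild or moderate cases after pick-up are recorded unevenly, the rates are too low. If recording or grading varies with knowledge of the arm, the comparison is biased, and a larger sample does not remove that.

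**Working it through.** **1. Schedule against visit lists.** The columns of Table X are set beside the data lists in Section 7.2. The AE ticks agree with the visits at which Section 7.2 lists AE recording, which supports this reading of the columns.

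| Contact | OHSS row | AE row | OHSS item in Section 7.2 |
|---|---|---|---|
| Triggering day | ticked | ticked | none |
| Oocyte pick-up | ticked | ticked | none |
| Fresh transfer | blank | ticked | none |
| FET | blank | blank | none |
| hCG test (11 to 17 days after transfer) | blank | ticked | none |
| Clinical pregnancy (4 to 6 weeks after transfer) | blank | ticked | none |
| Ongoing pregnancy, live birth | blank | ticked | none |
| End of observation | blank | blank | only as a reason for terminating treatment |

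Two things follow. After pick-up there are contacts with a general AE query but no OHSS assessment. Even at the two ticked visits, the data lists contain no OHSS field, definition or grade.

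**2. Women without a fresh transfer.** Under Section 7.2.5 they go to FET visits if embryos are frozen, and otherwise to End of Study procedures. Neither column carries an AE tick. For women with frozen embryos, the next AE-marked contact is the hCG test after the first FET.

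**3. The plan's own figure.** The plan gives no OHSS rate, power or sample size. Its sample size is for the cumulative live birth rate (CLBR) and it reproduces: (1.96 + 0.8416)² × 2 × 0.6 × 0.4 / 0.10² = 376.7, so 377 per arm; 377 / 0.85 = 443.5, so 444 per arm and 888 in total. The 444 is used below.

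**4. Equal under-capture (all OHSS inputs assumed).** Let f be the share of cases arising after pick-up and c the share of those captured by AE reporting. Observed rate = true rate × [(1 − f) + f × c]. Take f from 0.3 to 0.7 and c from 0.4 to 0.7, with 444 per arm and a two-sided 5% test.

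| Assumed true rates | Power, full capture | f = 0.3, c = 0.7 | f = 0.7, c = 0.4 |
|---|---|---|---|
| 10% vs 5% | 81% | 9.1% vs 4.55%: 77% | 5.8% vs 2.9%: 56% |
| 6% vs 3% | 58% | 5.46% vs 2.73%: 54% | 3.48% vs 1.74%: 37% |

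With c = 1 nothing is lost. With equal capture the risk ratio stays at 2.0 throughout; only the difference and the power shrink.

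**5. Capture that differs by arm (assumed).** Take 10% (agonist) and 5% (antagonist), with f = 0.5.

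- Capture 0.7 agonist, 0.4 antagonist: 10% × 0.85 = 8.5% and 5% × 0.70 = 3.5%, risk ratio 2.43.
- Capture reversed: 10% × 0.70 = 7.0% and 5% × 0.85 = 4.25%, risk ratio 1.65.

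The true ratio is 2.0, so the bias can go either way.

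**The case against.** The best defence is that the plan does look for later events. Subjects are actively queried at each visit, AE recording is listed at fresh transfer, hCG test and clinical pregnancy assessment, events are followed until they stabilise or the outcome is known (Section 7.4.1.6), and hospitalised cases must be reported within 24 hours. OHSS is also a listed reason for terminating treatment. Field-level detail may sit in the eCRF conventions or the Manual of Operations, which the protocol mentions but which are not part of these documents. And OHSS is one of 14 secondary endpoints meant to add description.

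Most of this stands and limits the point. A reader might infer that cases after pick-up depend on unsolicited reports or are simply lost; Sections 7.4.1.2 and 8.5.4 contradict that. A reader might also infer that lower OHSS is the main expected benefit, or what justifies the 10-point margin. The documents say neither: they report lower OHSS from earlier reviews and do not link the margin to it. Nor do they support a particular direction of bias.

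What the defence does not answer is that a general question is not an OHSS assessment, that the termination reason covers only women whose treatment ends for that cause, and that the severity part of the endpoint has no OHSS scale anywhere. Embryo quality, in the same list, does have a named consensus.

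**Conclusion.** The point holds as a measurement gap in a secondary endpoint. The stated schedule does not cover the endpoint's own window, and neither an OHSS case nor its severity is defined. Later cases can enter the data, but without a specific question or grade, and with the arm known to patients and staff.

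The size cannot be derived from the documents. Over the assumed ranges, equal under-capture takes power for the OHSS comparison from 81% to 56–77% (10% vs 5%) or from 58% to 37–54% (6% vs 3%); with complete AE capture the loss is nil. Unequal capture could move the risk ratio in either direction. The primary CLBR conclusion and the sample size of 888 are unaffected. This is a cheap improvement, not a flaw that threatens the trial's main claim.

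**What to change.** - Extend the OHSS row of the schedule to fresh embryo transfer, the hCG test and clinical pregnancy assessment.
- For women without a fresh transfer, record the same item at their next existing contact (first FET visit or End of Study telephone visit), asking back to oocyte pick-up. Ticks at the transfer and pregnancy visits alone would miss them.
- Use one eCRF item in both arms: OHSS yes/no, onset date, and grade on one named OHSS classification. Add it to the Section 7.2 data lists, including those for triggering day and pick-up.
- State one fresh-cycle window that does not depend on transfer or pregnancy status. Clinical pregnancy assessment mainly reaches hCG-positive women, so if the window runs past the hCG test, hCG-negative women need the same look-back at their next contact.
- Define the endpoint in Section 8.5.3, derive it from this item, and align Section 7.3.2 with the fresh-cycle wording.

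The cost is slightly more site work, some retrospective recall in women without a fresh transfer, and possibly higher reported OHSS rates. The change concerns measurement only and does not touch clinical management.
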